8.9.	Number of pain-free days
8.10.	Use of rescue medication
9.	SAFETY ANALYSES
9.1.	Adverse Events
9.2.	Physical Examinations
9.2.1.	Vital Signs
9.2.2.	Active-Standing Test
9.3.	Clinical Laboratory Values
9.4.	12-lead ECGs
10.	OTHER ANALYSES
10.1.	Interim Analyses
10.2.	Subgroup Analyses
11.	CHANGES IN PLANNED ANALYSES

12.	REFERENCES	.24
13.	TABLES, LISTINGS, AND FIGURES	.25

LIST OF ABBREVIATIONS

and the second	
AAPS	average abdominal pain score
AE	adverse event
ANCOVA	analysis of covariance
APS	abdominal pain score
AUC ₀₋₈	area under the plasma concentration-time curve from time zero to 8
	hours post-dose
BP	blood pressure
BMI	body mass index
bpm	beats per minute
2 53	
CI	confidence interval
C _{max}	maximum plasma concentration
CRP	C-reactive protein
CTCAE	Common Terminology Criteria for Adverse Events
DBL	database lock
DBP	diastolic blood pressure
ET	early termination
ECG	electrocardiogram
eCRF	electronic case report form
EOT	end-of-treatment
HR	heart rate
ICH	International Conference on Harmonization
IFN-g	interferon gamma
MedDRA	Medical Dictionary for Regulatory Activities
mmHg	millimeters of mercury
NRS	numerical rating scale
РК	pharmacokinetic(s)
PR	PR interval
PRN	as needed
PRO	patient-reported outcome
PT	preferred term
QTc	corrected QT interval
RR	inter-beat interval
SAE	serious adverse event

SAP	statistical analysis plan
STH	• 1
SBP	systolic blood pressure
SD	standard deviation
SES-CD	simple endoscopic score Crohn's disease
SOC	system organ class
TEAE	treatment-emergent adverse event
TID	3 times a day
t _{max}	time of maximum plasma concentration
TNF	tumor necrosis factor
WHO	World Health Organization
Wk	week

Statistical Analysis Plan Amendment 1: Summary of Changes

The original statistical analysis plan (SAP) was approved on 12 September 2018, prior to the database lock (DBL) on 14 September 2018. This SAP amendment reflects the following changes, which are being incorporated after the DBL (original 14 September 2018, relock 19 November 2018):

- Correct minor typographical errors and inconsistencies regarding the footnotes on the tables, figures, and listings.
- The evaluation of the pharmacokinetics of APD371 is outlined in a standalone pharmacokinetics SAP (dated 23 January 2019).
- The definitions of orthostatic hypotension and postural tachycardia (Section 9.2.2) have been clarified and impacted table and listing footnotes have been updated.
- The analysis populations have been added to titles of listings in Section 13.
- All tables, figures, and listings have been renumbered per ICH E3 "Structure and Content of Clinical Study Reports."
- Nine new tables, 4 new listings, and 5 new figures have been added:
 - o Table 14.1.6.2. Crohn's Disease Medical History (Safety Population)
 - o Table 14.2.4. Summary of Daily Abdominal Pain Scores (Efficacy Population)
 - Table 14.2.5. Summary of Average Abdominal Pain Score (AAPS) Analyses (Efficacy Population)
 - Table 14.2.6.3. Summary of Proportion of Pain Responders (Observed data) (Efficacy Population)
 - Table 14.2.6.4. Summary of Proportion of Pain Responders (Observed data) (Per Protocol Population)
 - Table 14.3.4.3.4. Summary of Categorical Change from Supine in Active Standing Test Vital Signs by Visit (Safety Population)
 - Table 14.3.4.3.5. Summary of Categorical Change from Supine in Active Standing Test Vital Signs by Visit – Alternative Categories (Safety Population)
 - Table 14.3.4.3.6. Summary of Categorical Change from Baseline in Active Standing Test Vital Signs by Visit (Safety Population)
 - Listing 16.2.2.1. Protocol Deviations Site Related (Enrolled Subjects)
 - Listing 16.2.2.2. Protocol Deviations Subject Related (Enrolled Subjects)
 - o Listing 16.2.6.8. Pharmacokinetic Blood Samples & Logs (Safety Population)

- 0
- Figure 14.2.3. Weekly Responders (%) by Treatment and Visit (Observed Data) (Efficacy Population)
- Figure 14.3.4.1. Active Standing Test Vital Signs by Treatment and Visit (Safety Population)
- Figure 14.3.4.2. Active Standing Test Vital Signs by Treatment and Visit Alternate (Safety Population)
- Figure 14.3.4.3. Individual Subject Active Standing Test Vital Sign Profiles (Safety Population)
- Figure 14.3.4.4. Individual Subject Active Standing Test Vital Sign Profiles Day 1 (Safety Population)

٠

1. INTRODUCTION

This statistical analysis plan (SAP) provides the statistical rationale and methods to be implemented during the analysis of data collected within the scope of clinical trial protocol APD371-004 to assess the tolerability and efficacy of APD371 in subjects with Crohn's disease (CD) experiencing abdominal pain.

The evaluation of the pharmacokinetics (PK) of APD371 is outlined in a standalone PK SAP (dated

23 January 2019)

This SAP has been written according to protocol APD371-004 Amendment 2, dated 10 August 2017.

2. STUDY OBJECTIVES

2.1. Primary Objective

To assess the tolerability and safety of two doses of APD371 in subjects with Crohn's disease (CD) experiencing abdominal pain treated for up to 8 weeks (Wks).

2.2. Exploratory Objectives

- To determine pharmacokinetic (PK) profiles (including metabolites) and average PK parameters (C_{max}, t_{max}, AUC₀₋₈) of two doses of APD371 three times a day (TID)
- To assess change in abdominal pain score (APS) from pre-dose (trough) to 1.5 hours post-dose (peak) following the first of 3 daily doses of APD371; assessed daily to Day 56 and averaged weekly to Wk 8
- To assess change in average abdominal pain score (AAPS) from Screening to Wk 8 (averaged weekly to Wk 8)
- To determine the proportion of subjects who are weekly responders
- To determine the proportion of subjects who are end-of-treatment (EOT) responders
- To determine the number of pain-free days per week in each treatment cohort, based on responses to the APS

- To assess pain medication use in each treatment cohort
- To assess the effect of APD371 treatment on reduction in C-Reactive Protein (CRP) and other biomarkers at Wk 4 and Wk 8
- To assess the effect of APD371 treatment on reduction in fecal calprotectin at Wk 4 and Wk 8

3. INVESTIGATIONAL PLAN

3.1. Overall Study Design and Plan

This is a Phase 2a study in subjects diagnosed with abdominal pain due to quiescent to mildly active CD. The study design is a randomized, multi center, open-label, parallel group comparison consisting of two cohorts dosed with APD371 in up to a total of 16 subjects (8 subjects in each cohort). Randomization will be stratified by sex. A study plan is provided in Figure 1.

SCREENING TREATMENT FU V5 VISIT SV1 SV2 V1 V2 V4 V6 V9 V3 V7 V8 WEEK W-4 W-1 W0 W0 W1 W2 W4 W6 W10 W8 W8 DAY -D-28 to D-1 -D7 to -D1 D1 D2 -D1 APD371 100 mg TID APD371 50 mg TID APD371 25 mg TID -- ---- APD371 25 mg BID

Figure 1. APD371-004 Study Plan

Subjects will enter a Screening period of up to 28 days during which they will record their APS on a diary card. If their AAPS is \geq 4 and they satisfy all other eligibility criteria, they will be randomized in a 1:1 ratio to receive APD371 doses of 25 mg or 100 mg capsules TID for 8 weeks (until Day 56). If subjects on APD371 100 mg TID experience hypotensive symptoms (systolic blood pressure [SBP] <90 or diastolic blood pressure [DBP] <50 mmHg) at any stage during study treatment, they will be titrated down to 50 mg TID.

Following the first day of treatment subjects will return for weekly safety and tolerability assessments for the first two weeks and then once every other week until the end of the treatment period. Safety assessments will include physical examinations, adverse event (AE) reporting, vital signs, 12-lead electrocardiograms (ECGs) and clinical laboratory tests including blood sampling.

Subjects will record their APS during Screening twice daily for at least 7 consecutive days within the Screening period (Day -28 to Day -1); early morning and late evening (approximately 06:00 - 08:00 and 20:00 - 22:00). During Treatment subjects will record their APS three times a

day on each treatment Day (Day 1 to Wk 8), before the morning dose, at 1.5 hours after the morning dose and before the evening dose.

Subjects will also record their stool frequency on a daily basis.

3.2. Study Duration and Dates

For each subject, the study duration will last a total of approximately 14 weeks consisting of a Screening period of up to 4 weeks, a Treatment period of 8 weeks and a follow-up period of two weeks.

Subjects will undergo screening procedures within 29 days prior to dosing. If eligibility is confirmed, subjects will be checked-in at the study site early morning on Day 1, they will overnight at the study site on Day 1 during which they will be randomized, treated with their first dose of APD371 and assessed for safety, tolerability, PK, and efficacy. They will then be allowed to return home 6 hours after the first dose of APD371 on Day 2.

3.3. Study Endpoints

3.3.1. Primary Endpoints

There is no primary endpoint in this study.

3.3.2. Exploratory Endpoints

3.3.2.1. Abdominal Pain Score (APS) and Average Abdominal Pain Score (AAPS)

The APS is a PRO using a numerical rating scale (NRS) which is recorded in a subject diary. The 11-point NRS scale ranges from 0 (no abdominal pain) to 10 (worst possible abdominal pain) will be recorded by subjects in a diary as follows;

During Screening Period

APS is recorded twice daily for at least 7 consecutive days within the Screening period (Day -28 to Day -1), at the following times:

- 1. Early morning, approximately 06:00 08:00
- 2. Late evening, approximately 20:00 22:00

To establish a baseline for AAPS the following procedure will be adopted:

The last diary entry prior to treatment will be identified. The 7 consecutive days that terminate with this last data point constitute the Screening reference period. Baseline for AAPS is the mean of non-missing pain scores within the Screening reference period.

During Treatment Period

APS is recorded three times a day on each treatment Day (Day 1 to 56) at the following times:

- 1. Before the morning dose and before any other morning dose study procedures (i.e., at trough APD371 concentration)
- 2. Approximately 1.5 hours after the morning dose (i.e., at peak APD371 concentration)
- 3. Before the evening dose (i.e., at evening trough ADP371 concentration)

Note: Subjects will also be required to complete the diary before their first morning dose on Wk 0 (Day 1), and at the EOT Visit at Wk 8 in the early morning (06:00 - 08:00). If a subject discontinues the study, ET, the APS score will be assessed.

It should be noted that:

- The AAPS is derived for each assessment period (Wks 1, 2, 4, 6, 8). For Wks 4, 6, and 8 scores are collected from the previous 7 days of diary entries prior to the visit day. 'Peak AAPS' is the mean of non-missing APS recorded at the time of peak concentration for those 7 days. Likewise, 'Trough APS' is the mean of non-missing APS recorded at the time of trough concentration for those 7 days. Similarly, 'Evening Trough APS' is the mean of non-missing APS recorded at the time of evening trough concentration for those 7 days. Wk 1 and Wk 2 peak, trough, evening trough, and overall AAPS are derived in a similar manner but note that:
 - For Wk 1, as Day 1 is neither peak nor trough, and APS scores cannot be accurately identified as pre-dose or post-dose, scores on Day 1 are disregarded. Hence, AAPS scores may be obtained from fewer than 7 days.
 - No APS score will contribute to more than 1 visit. Therefore, Wk 2 scores may be derived from fewer than 7 days (if the Wk 1 and Wk 2 Visits are less than 7 days apart).
 - Summary pain scores were auto-calculated and entered in the database. However, AAPS has been programmatically derived directly from the raw diary data using the above rules.

If a subject changes dose during the study, they will maintain their daily APS scoring.

3.3.2.2. Pain Relief Responders

Pain relief responders are defined as follows:

- A weekly pain relief responder at peak is defined as a subject who, in each week, has $\geq 30\%$ reduction in peak AAPS from their Baseline AAPS.
- A weekly pain relief responder at trough is defined as a subject who, in each week, has \geq 30% reduction in trough AAPS from their Baseline AAPS.
- A weekly pain relief responder at evening trough is defined as a subject who, in each week, has ≥30% reduction in evening trough AAPS from their Baseline AAPS.
- A weekly pain relief responder for average daily pain is defined as a subject who, in each week, has ≥30% reduction in average daily AAPS (averaged over peak, trough and evening trough diary entries) from their Baseline AAPS.
- An EOT pain relief responder at peak, trough, evening trough, and daily average is

defined as \geq 30% reduction in peak, trough and average daily AAPS respectively from Baseline at EOT.

3.3.2.5. C-Reactive Protein (CRP)

CRP is measured at Baseline, Wk 4, and Wk 8.

3.3.2.6. Fecal Calprotectin

A stool sample is collected at Screening, Wk 4, and Wk 8. Fecal calprotectin level is recorded.

3.3.2.8. Number of Pain-Free Days

The number of pain-free days per week is recorded by visit (Screening, Wks 1, 2, 4, 6, 8). The screening score will be derived from the last 7 days of the Screening period.

3.3.2.9. Pain Rescue Medication

Pain rescue medication use during Screening or the Treatment period is defined as prednisone at a dose of 40 mg orally daily or hyoscyamine at a dose of 0.25 mg TID or as needed (PRN).

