8.7.3 Pain relief responders

Proportion of subjects in each treatment cohort who are weekly responders will be summarized and difference between dose cohort will be reported.

Proportion of subjects in each treatment arm who are end-of-treatment responders will be summarized and difference between dose cohort will be reported.

Other exploratory efficacy measure listed in Section 2.2 will be summarized and difference between dose cohort will be reported:

- The number of pain-free days per week in each treatment cohort, based on responses to the APS
- Pain rescue medication use in each dose arm

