Title: Vice President, Regulatory Affairs and Quality Date: Thursday, 10 August 2017, 04:19 PM Pacific Daylight Time Meaning: Approval

UserName:

Title: EVP, Research & Development Date: Thursday, 10 August 2017, 04:43 PM Pacific Daylight Time Meaning: Approval

UserName: Title: Vice President, Clinical Development Date: Friday, 11 August 2017, 07:45 AM Pacific Daylight Time Meaning: Approval

APD371-004 AMENDMENT 02 SUMMARY OF CHANGES

Protocol Number: APD371-004 Protocol Amendment 02

Protocol Title: A Randomized, Open-label, Parallel, Phase 2a Study to Determine the Tolerability, Pharmacokinetics, and Efficacy of APD371 in Subjects with Crohn's disease experiencing Abdominal Pain

Amendment Date: 10 August 2017

APD371-004 Amendment 02 (10 August 2017) Summary of Changes

PAGE(S)	PROTOCOL CHANGE DESCRIPTION	RATIONALE
Throughout	Minor administrative and formatting changes were made	Not applicable
1	TITLE PAGE -Sponsor Contact Previously read: Associate Director, Clinical Operations Arena Pharmaceuticals, Inc. [name] Phone: Email: Now reads: Head of Clinical Operation Arena Pharmaceuticals, Inc. [name] Phone: Email: Base of Clinical Operation Arena Pharmaceuticals, Inc. [name] Phone: Email:	Administrative change
1	TITLE PAGE Added: Amendment 02 08 August 2017	Administrative change
2	SYNOPSIS – Name of Sponsor Medical Contact Previously read: MD Arena Pharmaceuticals Development GmbH [name] Phone: Email:	Administrative change

	Now reads: MD, PhD Arena Pharmaceuticals, Inc. [name] United States of America (USA) Phone: Email:	
3	SYNOPSIS – Objectives, Exploratory Objectives	
3	and	
and	2.2 Exploratory Objectives	
20	Added:	
20		
2	SYNOPSIS – Objectives, Exploratory Objectives	Use of standard of care pain
3	and	medication, including narcotics, is being allowed in this protocol
and	2.2 Exploratory Objectives	amendment (see Inclusion
•	Previously read:	Criteria #9). A decrease in the use
20	Pain rescue medication use	of pain medication will be considered one of the exploratory
	Now reads:	efficacy endpoints for APD371.
	Pain medication use	
3	SYNOPSIS – Objectives, Exploratory Objectives	Since the CB2 receptor is mainly
5	and 2.2 Exploratory Objectives	expressed in immune cells, additional immune and
and		inflammation-related biomarkers

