7. TREATMENT AND MEDICATIONS

7.1. Prior and Concomitant Medications

Medications administered prior to but not during study treatment were considered as prior medications. Medications initiated prior to start of study treatment and maintained during the study, or taken during the course of the study, were considered as concomitant medications. Medications with partial or missing start dates were assumed to be concomitant medications, unless there was clear evidence) to suggest that the medications were not taken during study. Prior and concomitant medications will be coded using the World Health Organization (WHO) Drug Dictionary (March 2018).

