8.10. Use of Rescue Medication

The number of subjects using rescue medication during the Screening period and at any time during active treatment will be tabulated by treatment group and overall by shift table. Because of the paucity of data with respect to changes, no inferential analyses will be conducted.

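### The objective is pain medication use, but the visible analysis covers two rescue drugs, so change in analgesic use cannot be read from the planned tables (minor)

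*SAP*

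**What the plan says.** **Objective.** SAP 2.2 reads "To assess pain medication use in each treatment cohort", and Protocol 2.2 agrees. The Amendment 02 summary of changes records that this replaced an objective limited to rescue medication. The reason given is that standard-of-care analgesics, narcotics among them, are now allowed, and that a decrease in the use "of pain medication will be considered one of the exploratory" efficacy endpoints.

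**Analysis in the protocol.** The lead-in in Section 8.7.3 is broad: "Other exploratory efficacy measure listed in Section 2.2 will be summarized and difference between dose cohort will be reported". The bullet beneath it is narrower: "Pain rescue medication use in each dose arm".

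**Analysis in the SAP.** Section 3.3.2.9 gives the definition: "Pain rescue medication use during Screening or the Treatment period is defined as prednisone at a dose of 40 mg orally daily or hyoscyamine". Section 8.10 gives the summary, a shift table by treatment group and overall: "The number of subjects using rescue medication during the Screening period and at any time during active treatment will be tabulated". It adds: "Because of the paucity of data with respect to changes, no inferential analyses will be conducted". The output is Table 14.2.8.

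**Other analgesics.** Protocol 4.9.2 permits NSAIDs, narcotic analgesics and acetaminophen, with doses stable from 2 weeks before screening until the end of the study. In the visible SAP these drugs can appear only in Tables 14.1.7 (prior) and 14.1.8 (concomitant) and the matching listings. SAP 7.1 sets the classes. The sentence that defines the concomitant class begins: "Medications initiated prior to start of study treatment and maintained during the study, or taken during the course of the study, were considered as". The prior class holds drugs taken before but not during treatment.

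**The concern.** Amendment 02 changed the objective because of one group of drugs, and that group has no endpoint definition and no summary of its own in the visible plan. The SAP states that it was written to Amendment 2, so it should follow the wider wording. As it stands, a reader who wants to know whether subjects took less analgesia on APD371 would have to work it out from subject listings.

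A second, smaller matter concerns the measure that is analysed. Any use is counted over Screening on one side and over a period at least twice as long on the other. A subject who takes rescue now and then, at a steady rate, has more chance to be counted on treatment than in Screening.

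**Working it through.** **1. Scope, set side by side**

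| Place | Drugs covered | Shows change? |
|---|---|---|
| Protocol 2.2, SAP 2.2 | pain medication | objective says use |
| Amendment 02 rationale | pain medication, including narcotics | names a decrease |
| Protocol 8.7.3, bullet | rescue medication | not specified |
| SAP 3.3.2.9, 8.10, Table 14.2.8 | prednisone 40 mg, hyoscyamine | yes/no shift, these two only |
| SAP 7.1, Tables 14.1.7 and 14.1.8 | all medications | no |

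Under SAP 7.1 three subjects fall into the same concomitant class: one who continues an analgesic unchanged, one who takes less of it, and one who starts it on treatment. No dose, frequency or change summary is described. Only an analgesic stopped before treatment is separated, as a prior medication, and that class also holds more distant use.

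**2. Unequal periods**

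There is no figure in the plan to reproduce: no rescue rate and no sample size calculation are given. The inputs from the documents are Screening of up to 4 weeks, treatment of 8 weeks and about 16 subjects. The period ratio is 56/28 = 2, and larger if actual Screening is shorter. Two inputs are assumed: weekly probability of any rescue use h (2%, 5%, 10%) and within-subject correlation between weeks ρ (0 to 1). There is no true change in any scenario.

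- Independent weeks: P0(k) = (1 − h)^k, the probability of no use in k weeks.
- Correlated weeks (beta-binomial): a = h(1/ρ − 1), b = (1 − h)(1/ρ − 1), P0(k) = product over i = 0 to k−1 of (b + i)/(a + b + i).
- Habitual use (ρ = 1): P0(k) = 1 − h for every k.
- Any use = 1 − P0(k). No-to-yes shifts = 16[P0(4) − P0(12)]; yes-to-no shifts = 16[P0(8) − P0(12)]; net rise = 16[P0(4) − P0(8)].

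Example, h = 5% and ρ = 0.5 (a = 0.05, b = 0.95): P0(4) = 0.95 × 1.95/2 × 2.95/3 × 3.95/4 = 0.8994, so any use in 4 weeks is 10.1%. P0(8) = 0.8712, so any use in 8 weeks is 12.9%. Net rise = 16 × (0.8994 − 0.8712) = 0.45.

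Results at h = 5%:

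| ρ | Any use, 4 wk | Any use, 8 wk | No-to-yes | Yes-to-no |
|---|---|---|---|---|
| 0 | 18.5% | 33.7% | 4.39 | 1.97 |
| 0.2 | 14.4% | 21.4% | 1.87 | 0.73 |
| 0.5 | 10.1% | 12.9% | 0.72 | 0.27 |
| 1 | 5.0% | 5.0% | 0 | 0 |

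Net apparent rise among 16 subjects:

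| h | ρ = 0 | ρ = 0.5 | ρ = 1 |
|---|---|---|---|
| 2% | 1.15 | 0.19 | 0 |
| 5% | 2.42 | 0.45 | 0 |
| 10% | 3.61 | 0.80 | 0 |

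**3. Which rows fit the SAP's own remark**

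SAP 8.10 reports few changes. At h = 5%, independence implies 4.39 + 1.97 = 6.4 changers of 16, which fits poorly. At ρ = 0.5 it is 0.72 + 0.27, about 1 of 16, which fits better. A prednisone course tapered by the week also makes independent weeks implausible.

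**4. A real fall can be hidden**

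If use occurs at a constant rate with independent days, any use over 28 days of p becomes 1 − (1 − p)^(½ × 56/28) = p when the daily rate is truly halved. The table would then show no change.

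**The case against.** Several points on the other side stand.

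- A reader might infer that the objective is left with no summary at all. That goes too far. The objective says use, not change, and Tables 14.1.7 and 14.1.8 are summary tables that would show which analgesics were taken. What is missing is any view of change.
- A reader might infer that the protocol contradicts itself, since analgesic doses must stay stable while a decrease is an endpoint. The documents do not establish this. The decrease is named only in the Amendment 02 rationale, not in the objectives or any visible analysis section. The rationale also points to inclusion criterion 9, which is not visible and may settle the matter. The rationale does explain current wording, so a request to reconcile the two remains fair.
- A reader might infer that rescue use is inflated by several subjects. That needs independent weeks, which sit badly with SAP 8.10.
- The unequal periods apply equally to both doses, so they do not by themselves affect the dose comparison that Protocol 8.7.3 asks for. The periods are also plainly labelled and nothing is tested.
- A reader might infer that rescue distorts the pain, responder, CRP or calprotectin results. No visible rule addresses this. But rescue is allowed in Screening too, so neither direction nor size can be stated, and using observed data regardless of rescue is a legitimate choice.

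None of this answers the main point: the objective was widened, and the definition and analysis were not.

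**Conclusion.** The point holds, at minor severity. On the visible text, following the plan shows which analgesics were taken but not whether their use changed, although the drugs in question are the reason the objective was reworded. Some SAP subsections and inclusion criterion 9 are not visible, so the conclusion is limited to what can be read.

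The unequal-period effect is real in direction for intermittent use and unknown in size. Under the assumed 2% to 10% weekly use and correlation 0.5 it is about 0.2 to 0.8 of 16 subjects, and zero for habitual use. It calls for a caution on reading one descriptive table. The measure is exploratory and no error rate is involved.

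**What to change.** 1. Keep Table 14.2.8 and footnote that Screening covers up to 4 weeks and treatment 8 weeks.
2. Add one descriptive table, labelled post hoc because this SAP version follows database lock. Build it from the concomitant-medication records: NSAIDs, narcotics, acetaminophen and hyoscyamine, with rescue prednisone on a separate line.
3. Compare the 7-day screening reference period of SAP 3.3.2.1 with each assessment week (Weeks 1, 2, 4, 6 and 8), by dose and overall, with the between-dose difference that Protocol 8.7.3 calls for. Give days of use over days in the window, since Weeks 1 and 2 may hold fewer than 7 days; where dates are missing, give any use per week.
4. Align the wording of Protocol 8.7.3 and SAP 3.3.2.9 and 8.10 with the objective.
5. State how the stable-dose rule in Protocol 4.9.2 and the decrease in the Amendment 02 rationale are to be reconciled, with reference to inclusion criterion 9, so that a fall in use can be interpreted.

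**Cost.** SAP text and one table from data already collected. The table will be sparse in about 16 subjects: at an assumed 5% weekly rescue use, a 7-day window expects 16 × 0.05 = 0.8 rescue users. It also leaves out up to 28 − 7 = 21 screening days, and Weeks 3, 5 and 7. Start and stop dates are recorded only where known, so some as-needed use may support no more than any use per week.
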